6.2.1 General guidelines for dose modifications

- For grade 1 and tolerable grade 2 treatment-related toxicities, with the exception of pneumonitis, patients may continue at the current dose of ribociclib+everolimus treatment.
- For intolerable grade 2 treatment-related toxicities as those that are irreversible (e.g., neurotoxicities, ocular toxicities, or cardiac toxicities) or prolonged grade 2 toxicities (i.e., those lasting longer than 14 days), or any grade 3 toxicities, with the exception of pneumonitis, dosing should be interrupted until resolution to grade 1 or lower followed by resumption of a new 28 days regimen. Dosing reductions could also be considered after grade 3 toxicities ([Table 11](#)).
- For any grade 4 toxicity, dosing should be interrupted and the patients should be followed until the toxicity resolution to baseline levels, grade 1, or become stable. Following recovery from grade 4 events, **no additional ribociclib+everolimus treatment** should be given to the patient except for neutropenia and thrombocytopenia (details in [Table 11](#)).

More detailed ribociclib and everolimus dose modification guidelines are described in Section [6.2.2](#) respectively for selected toxicities. Any variance from these guidelines in view of patient safety must first be discussed with the Sponsor unless there is an urgent need for action.

Initial Version date: 10/16/2018

Revision date: 03/11/2019, 5/07/2019, 09/26/2019, 03/17/2020, 08/26/2024

All dose modifications, interruptions or discontinuations must be based on the worst preceding toxicity as graded by the NCI Clinical Toxicity Criteria version 4.03.

Patients whose treatment is interrupted or permanently discontinued due to an AE must be followed until resolution or stabilization of the event. Patients with more than 1 interruption should be discontinued from ribociclib treatment.

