6.2.3 Follow-up for toxicities

An unscheduled visit should be performed in all cases below where toxicity monitoring is recommended more frequently than defined by the schedule of assessments.

Ongoing SAEs at the final safety evaluation visit or the end of study treatment visit (whichever is later) should be followed until they improve becoming non-serious events, stabilize, or return to baseline levels. Refer to [Section 8.2](#) for SAE.

Table 11 Criteria for post-tumor resection interruption and re-initiation of ribociclib+everolimus treatment

Worst toxicity (CTCAE 4.03 Grade)*	Regimen Modifications for Ribociclib Management Recommendations	Regimen Modifications for Everolimus Management Recommendations
HEMATOLOGICAL		
Anemia		
Grade 1 (Hemoglobin (Hgb) <LLN - 10.0 g/dL; <LLN - 6.2 mmol/L; <LLN - 100 g/L)	Continue regimen	Continue regimen
Grade 2 (Hgb <10.0 - 8.0 g/dL; <6.2 - 4.9 mmol/L; <100 - 80g/L)	Continue regimen	Continue regimen
Grade 3 (Hgb <8.0 g/dL; <4.9 mmol/L;	Dose interruption until recovery to grade ≤ 1. Re-initiate ribociclib at the same dose.	Dose interruption until recovery to grade ≤ 1. Re-initiate everolimus at the same dose.
Grade 4 (transfusion indicated Life-threatening)	Discontinue ribociclib	Discontinue everolimus
Neutropenia (ANC)		
Grade 1 (ANC < LLN - 1.5 x 10 ⁹ /L)	Continue regimen	Continue regimen
Grade 2 (ANC < 1.5 and ≥ 1.0 x 10 ⁹ /L)	Continue regimen	Continue regimen
Grade 3 (ANC < 1.0 and ≥ 0.5 x 10 ⁹ /L)	Dose interruption until recovery to ≥1.0x10 ⁹ /L (≤grade 2). Re-initiate ribociclib at the same dose level. If toxicity recurs at grade 3, temporary dose interruption until recovery to ≥1.0x10 ⁹ /L (≤grade 2). If resolved in ≤7 days, then maintain dose level. If resolved in >7 days, then reduce ribociclib dose to the next lower dose level.	Dose interruption until recovery to grade ≤2. Re-initiate everolimus at the same dose level. If ribociclib is interrupted/ discontinued, everolimus should also be interrupted/discontinued. Resume everolimus at same dose level if ribociclib is resumed at either the same or lower dose.
Grade 4 (ANC < 0.5 x 10 ⁹ /L)	Dose interruption until recovery to ≥1.0x10 ⁹ /L. Re-initiate ribociclib at the next lower dose level. If toxicity recurs at grade 4, discontinue ribociclib+everolimus	Dose interruption until recovery to grade ≤2. Re-initiate everolimus at the next lower dose level. If toxicity recurs at grade 4, discontinue ribociclib+everolimus

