Febrile neutropenia Grade 3 (ANC < 1.0 x 10 ⁹ /L, with a single temperature of ≥ 38.3 °C (101°F) or a sustained temperature of ≥ 38 °C (100.4°F) for more than one hour)	Dose interruption until improvement of ANC ≥1.0x10 ⁹ /L (≤Grade 2) and no fever. Restart at the next lower dose level. If febrile neutropenia recurs, discontinue ribociclib +everolimus.	Dose interruption until improvement of ANC ≥1.0x10 ⁹ /L (≤Grade 2) and no fever. Re-initiate everolimus at the next lower dose level. If febrile neutropenia recurs, discontinue ribociclib +everolimus.
Febrile neutropenia Grade 4 Life-threatening consequences; urgent intervention indicated	Discontinue treatment.	Discontinue treatment.

Worst toxicity (CTCAE 4.03 Grade)*	Regimen Modifications for Ribociclib Management Recommendations	Regimen Modifications for Everolimus Management Recommendations
Thrombocytopenia		
Grade 1 (PLT < LLN - $75 \times 10^9/L$)	Continue regimen	Continue regimen
Grade 2 (PLT < 75 and $\geq 50 \times 10^9/L$)	Dose interruption until recovery to grade ≤ 1 . Re-initiate ribociclib at the same dose.	Dose interruption until recovery to grade ≤ 1 . Re-initiate everolimus at the same dose.
Grade 3 (PLT < 50 and $\geq 25 \times 10^9/L$)	Dose interruption until recovery to grade ≤ 1 . Re-initiate ribociclib at the same dose level. If toxicity recurs at grade 3, temporary dose interruption until recovery to grade ≤ 1 and reduce ribociclib to the next lower dose level.	Dose interruption until recovery to grade ≤ 1 . Re-initiate everolimus at the next lower dose level. If toxicity recurs at grade 3, temporary dose interruption until recovery to grade ≤ 1 and reduce everolimus to the next lower dose level.
Grade 4 (PLT < $25 \times 10^9/L$)	Dose interruption until recovery to grade ≤ 1 . Re-initiate ribociclib at the next lower dose level. If toxicity recurs at grade 4: discontinue ribociclib	Dose interruption until recovery to grade ≤ 1 . Re-initiate everolimus at the next lower dose level. If toxicity recurs at grade 4: discontinue everolimus

Worst toxicity (CTCAE 4.03 Grade)*	Regimen Modifications for Ribociclib Management Recommendations	Regimen Modifications for Everolimus Management Recommendations
HEPATOTOXICITY (BILIRUBIN, SGPT/ALT, SGOT/AST)		
Total Bilirubin** without ALT/AST increase above baseline value (for patients with Gilbert Syndrome these dose modifications apply to changes in direct (conjugated) bilirubin only)		

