Grade 2 (QTc 481-500 ms)	
Interrupt ribociclib. Perform steps 1-4 as directed in "For All Grades."
 
Perform a repeat ECG one hour after the first QTcF of ≥ 481 ms.
 
• If QTcF < 481 ms, restart ribociclib at the same dose. No dose adjustment required for first occurrence.• If QTcF remains ≥ 481 ms, repeat ECG as clinically indicated until the QTcF returns to < 481 ms. Ribociclib should be reduced by 1 dose level• If QTcF ≥ 481 ms recurs, ribociclib should again be reduced by 1 dose level. 
Repeat ECGs 7 days and 14 days after dose resumption (then as clinically indicated) for any patient who has therapy interrupted due to QTcF ≥ 481 ms.
	If ribociclib is interrupted/discontinued, everolimus should also be interrupted/discontinued. Resume everolimus at same dose level if ribociclib is resumed at same or lower dose level.

Worst toxicity (CTCAE 4.03 Grade)*	Regimen Modifications for Ribociclib Management Recommendations	Regimen Modifications for Everolimus Management Recommendations
Grade 3 (QTc \geq 501 ms on at least two separate ECGs)	
Interrupt ribociclib. Perform steps 1-4 as directed in "For All Grades."
 
Perform a repeat ECG within one hour of the first QTcF of \geq501 ms.
 
• If QTcF remains \geq501 ms, consult with a cardiologist (or qualified specialist) and repeat cardiac monitoring as indicated until the QTcF returns to $<$481 ms.• If QTcF returns to $<$481 ms, ribociclib should be reduced by 1 dose level (please refer to the dosing schedule table).• If QTcF remains \geq 481 ms after performing steps 1-4 as directed in "For All Grades," discontinue ribociclib. 
Repeat ECGs 7 days and 14 days after dose resumption for any patient who has therapy interrupted due to QTcF \geq501 ms.
 
If QTcF of \geq501 ms recurs, discontinue ribociclib
	If ribociclib is interrupted/discontinued, everolimus should also be interrupted/discontinued. Resume everolimus at same dose level if ribociclib is resumed at lower dose level.
Grade 4 (QT/QTc \geq 501 or $>$ 60 ms change from baseline and Torsades de pointes or polymorphic ventricular tachycardia, or signs/symptoms of serious arrhythmia, unexplained syncope)	
Discontinue ribociclib+everolimus. Perform steps 1-4 as directed in "For All Grades."
 
Obtain local cardiologist consultation (or qualified specialist) and repeat cardiac monitoring as indicated until the QTcF returns to $<$481 ms.
	

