Worst toxicity (CTCAE 4.03 Grade)*	Regimen Modifications for Ribociclib Management Recommendations	Regimen Modifications for Everolimus Management Recommendations
Stomatitis		
Grade 1 Minimal symptoms; normal diet	No dose adjustment required. Manage with non-alcoholic or salt water (0.9%) mouthwash several times per day	
Grade 2 Symptomatic but can eat and swallow modified diet	If everolimus is interrupted/discontinued, ribociclib should also be interrupted/discontinued. Resume ribociclib at same dose level if everolimus is resumed at same or lower dose level.	Interrupt everolimus until recovery to Grade ≤ 1. Reinitiate everolimus at same dose. If recurs at Grade 2, interrupt dose until recover to Grade ≤ 1. Resume at 50% of previous dose; change to every other day dosing if the reduced dose is lower than the lowest available strength. Manage with topical analgesic mouth treatments.
Grade 3 Symptomatic and unable to adequately eat or hydrate orally	If everolimus is interrupted/discontinued, ribociclib should also be interrupted/discontinued. Resume ribociclib at same dose level if everolimus is resumed at lower dose level.	Dose interruption of everolimus until recovery to Grade < 1. Resume at 50% of previous dose; change to every other day dosing if the reduced dose is lower than the lowest available strength.
Grade 4 Symptoms associated with life-threatening consequences	Discontinue ribociclib+everolimus	Discontinue everolimus and treat with appropriate medical therapy
Non-infectious pneumonitis		
Grade 1 Asymptomatic, radiographic findings only	No dose adjustment required. Initiate appropriate monitoring.	
Grade 2 Symptomatic but not interfering with Activities of Daily Living (ADL)	If everolimus is interrupted/discontinued, ribociclib should also be interrupted/discontinued. Resume ribociclib at same dose level if everolimus is resumed at same or lower dose.	Consider dose interruption of everolimus. Rule out infection and consider treatment with corticosteroids until symptoms improve to Grade < 1 Resume at 50% of previous dose; change to every other day dosing if the reduced dose is lower than the lowest available strength. Discontinue everolimus if failure to recover within 4 weeks.

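### Section 6.2.1 ends ribociclib after a second interruption, while Table 11 continues it after a second interruption for recurrent Grade 3 neutropenia and thrombocytopenia, and no text says which governs

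*Combined protocol and SAP*

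**What the plan says.** Section 6.2.1 gives general guidelines for Phase 2 dose modification. It closes with a limit: "Patients with more than 1 interruption should be discontinued from ribociclib treatment". No grade, toxicity or cause is exempted. For Grade 3 toxicities other than pneumonitis, the same section says "dosing should be interrupted until resolution to grade 1 or lower followed by resumption of a new 28 days regimen".

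Section 6.2.2 names Table 11 as the guide to interruption and re-initiation. Its ribociclib column says, for Grade 3 neutropenia, "If toxicity recurs at grade 3, temporary dose interruption until recovery to" an ANC of at least 1.0 x 10^9/L, which the table equates with Grade 2 or lower. It continues: "If resolved in ≤7 days, then maintain dose level. If resolved in >7 days, then reduce ribociclib dose to the next lower dose level". For Grade 3 thrombocytopenia it says "If toxicity recurs at grade 3, temporary dose interruption until recovery to grade ≤ 1 and reduce ribociclib to the next lower dose level".

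For Grade 2 QTcF prolongation, where each event begins with an interruption, the table says "If QTcF ≥ 481 ms recurs, ribociclib should again be reduced by 1 dose level". In the stomatitis row and other rows driven by everolimus toxicity, the ribociclib column says "If everolimus is interrupted/discontinued, ribociclib should also be interrupted/discontinued" and then allows ribociclib to resume when everolimus does.

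**The concern.** The limit in 6.2.1 and the recurrence instructions in Table 11 are both operative, and they apply to the same patients. When a toxicity recurs and ribociclib is held a second time, one text takes the patient off the drug and the other brings the patient back onto it. A site that follows either text departs from the other.

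Time on treatment, the discontinuation rate and the tolerability record would then depend partly on which page a site reads. Up to 3 sites may enroll, so handling could differ between them. Drug-related toxicity and PFS are secondary endpoints. Their summaries could mix patients stopped by rule with patients re-treated after the same event.

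**Working it through.** No sample size, power or error rate is involved. The check compares the 6.2.1 limit (more than 1 interruption means ribociclib is discontinued) with what Table 11 orders for ribociclib on recurrence, row by row.

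| Table 11 row, on recurrence | What Table 11 does with ribociclib | Against 6.2.1 |
|---|---|---|
| Neutropenia Grade 3 | Second interruption, then same or next lower level | Explicit conflict |
| Thrombocytopenia Grade 3 | Second interruption, then next lower level | Explicit conflict |
| Bilirubin Grade 2 | Reduce one level; discontinue only on recurrence after a reduction or if recovery exceeds 28 days | Implied: the row opens with an interruption |
| AST/ALT Grade 2 | Reduce one level; same discontinuation conditions | Implied, same reason |
| QTcF Grade 2 | Reduce one further level | Implied, same reason |
| Stomatitis Grade 2 | Everolimus held a second time and resumed; ribociclib follows | Through the everolimus link only |
| Other non-hematologic Grade 2 | As for stomatitis | Through the everolimus link only |
| Neutropenia Grade 4 | Discontinue | Agree |
| Febrile neutropenia Grade 3 | Discontinue | Agree |
| Thrombocytopenia Grade 4 | Discontinue | Agree |
| QTcF of 501 ms or more | Discontinue | Agree |

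Count of conflicting rows: 2 explicit + 3 implied + 2 by linkage = 7. Only the first two state a second ribociclib interruption outright in the ribociclib column.

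**Worked case.** A Phase 2 patient has Grade 3 neutropenia (interruption 1), recovers and restarts at the same dose. Grade 3 neutropenia recurs (interruption 2) and resolves within 7 days. The count is 2, and 2 > 1, so 6.2.1 discontinues ribociclib. Table 11 keeps the patient on the same dose level.

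**How interruptions are counted.** 6.2.1 does not say whether the count is per toxicity or in total. The two explicit rows conflict either way, because the same toxicity recurs in each.

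**Recovery grade.** Table 11 defines Grade 2 neutropenia as an ANC below 1.5 and at least 1.0 x 10^9/L. A patient at 1.2 x 10^9/L after a Grade 3 episode is therefore at Grade 2. Table 11 allows a restart; 6.2.1 keeps the patient on hold until Grade 1 or lower. The thrombocytopenia row asks for Grade 1 or lower, so this second difference does not arise there.

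**Search for precedence.** 6.2.1 points to more detailed guidance in 6.2.2 for selected toxicities but does not say that this guidance overrides the limit. Its one exception that defers to Table 11, for neutropenia and thrombocytopenia, concerns re-treatment after Grade 4 events. No exception is attached to the interruption limit.

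**The case against.** The strongest reply is that the specific rule beats the general one. 6.2.1 is labelled general, uses the word should, and refers onward to detailed rules. Section 6.2 says that adjustments exist so that patients can stay on treatment. Departures from the guidelines must also be discussed with the sponsor unless the need is urgent, which puts most of them before one decision-maker.

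This is a natural reading, and it would largely settle the difference in recovery grade. But the documents never state it. It would also leave the interruption limit without effect in the conflicting rows, and it would not settle two holds for different toxicities. The sponsor discussion helps only if a site notices that it is departing from one of the two texts.

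Three further objections stand and limit the point:

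- **Reach.** A reader might infer that Table 11 contradicts 6.2.1 throughout, or that two brief everolimus holds certainly end ribociclib. Neither is supported. The texts agree in four recurrence rows. The sentence just before the limit concerns interruptions due to an adverse event, and whether holds triggered only by everolimus count is an open question.
- **RP2D.** A reader might infer that the RP2D could change. Under Sections 4.1.2 and 6.1.3 and the notes to Table 7, it rests on DLT counts, with the Phase 2 window limited to the first 28-day cycle. No Table 9 criterion counts a second interruption or a ribociclib discontinuation as such. Those on a missed dose or delayed cycle sit in the non-hematologic row and turn on the toxicity itself.
- **PFS.** It is a secondary endpoint in a group that Section 9.7.1 calls exploratory, with no formal comparison.

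**Conclusion.** The protocol is wrong as written on this point: two operative instructions treat the same patient in opposite ways, and no rule decides between them. The conflict is explicit for recurrent Grade 3 neutropenia and recurrent Grade 3 thrombocytopenia, and implied or indirect in five other rows. The recovery grade after Grade 3 neutropenia is a separate, smaller inconsistency.

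The consequence lies in exposure, discontinuation and tolerability data for Phase 2. Section 9.7.1 expects 3 to 12 patients there, so one patient is 1/12 = 8% to 1/3 = 33% of the group. That range is simple division, not a forecast: the documents give no frequency of second interruptions. No effect on the RP2D is shown, and any effect on PFS is confined to how a descriptive result is read.

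The conclusion rests on reading the interruption limit as it stands, with no unstated exception.

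**What to change.** The sponsor should reconcile Section 6.2.1 with Table 11 and state:

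- which of the two governs when they differ;
- how interruptions are counted, per toxicity or in total;
- whether a ribociclib hold triggered only by an everolimus hold counts;
- one consistent recovery requirement after Grade 3 neutropenia.

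Which clinical rule stands is for the sponsor to decide; this review takes no position. The cost is a wording amendment, with no added procedures.

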6.2.2 Dose modification and dose delay of ribociclib+everolimus

Guidelines for dose, modifications, interruptions and re-initiation of ribociclib+everolimus treatment are described in [Table 11](#). The following are the dose modification levels in [Table 10](#).

Table 10 Dose Modification Levels

Ribociclib	
Dose	Number of tablets & strength
200 mg (qd)*	1 x 200 mg tablet
400 mg (qd)	2 x 200 mg tablet
600 mg (qd)	3 x 200 mg tablet

* One dose de-escalation will be allowed below dose level 0 if needed as a dose modification.

Everolimus	
Dose	Number of tablets & strength
2.5 mg every other day (qod)*	1 x 2.5 mg tablet
2.5 mg daily (qd)	1 x 2.5 mg tablet
5 mg daily (qd)	2x 2.5 mg tablet
10 mg (qd)	4x 2.5 mg tablet

Everolimus- for Dose Levels 4-6 and possible dose reductions	
Dose	Number of tablets & strength
25 mg (1/weekly) – 50% of dose level 4	2 x 10 mg tablet and 2 x 2.5mg tablet
30 mg (1/weekly) - 50% of dose level 5	3 x 10 mg tablet
35 mg (1/weekly) - 50% of dose level 6	3 x 10 mg tablet and 2 x 2.5mg tablet
40 mg (1/weekly) – 1 dose reduction from dose level 4	4 x 10 mg tablet
50 mg (1/weekly) – 1 dose reduction from dose level 5	5 x 10 mg tablet
60 mg (1/weekly) – 1 dose reduction from dose level 6	6 x 10 mg tablet
70 mg (1/weekly)	7 x 10 mg tablet

6.2.3 Follow-up for toxicities

An unscheduled visit should be performed in all cases below where toxicity monitoring is recommended more frequently than defined by the schedule of assessments.

Ongoing SAEs at the final safety evaluation visit or the end of study treatment visit (whichever is later) should be followed until they improve becoming non-serious events, stabilize, or return to baseline levels. Refer to [Section 8.2](#) for SAE.

Table 11 Criteria for post-tumor resection interruption and re-initiation of ribociclib+everolimus treatment

Worst toxicity (CTCAE 4.03 Grade)*	Regimen Modifications for Ribociclib Management Recommendations	Regimen Modifications for Everolimus Management Recommendations
HEMATOLOGICAL		
Anemia		
Grade 1 (Hemoglobin (Hgb) <LLN - 10.0 g/dL; <LLN - 6.2 mmol/L; <LLN - 100 g/L)	Continue regimen	Continue regimen
Grade 2 (Hgb <10.0 - 8.0 g/dL; <6.2 - 4.9 mmol/L; <100 - 80g/L)	Continue regimen	Continue regimen
Grade 3 (Hgb <8.0 g/dL; <4.9 mmol/L;	Dose interruption until recovery to grade ≤ 1. Re-initiate ribociclib at the same dose.	Dose interruption until recovery to grade ≤ 1. Re-initiate everolimus at the same dose.
Grade 4 (transfusion indicated Life-threatening)	Discontinue ribociclib	Discontinue everolimus
Neutropenia (ANC)		
Grade 1 (ANC < LLN - 1.5 x 10 ⁹ /L)	Continue regimen	Continue regimen
Grade 2 (ANC < 1.5 and ≥ 1.0 x 10 ⁹ /L)	Continue regimen	Continue regimen
Grade 3 (ANC < 1.0 and ≥ 0.5 x 10 ⁹ /L)	Dose interruption until recovery to ≥1.0x10 ⁹ /L (≤grade 2). Re-initiate ribociclib at the same dose level. If toxicity recurs at grade 3, temporary dose interruption until recovery to ≥1.0x10 ⁹ /L (≤grade 2). If resolved in ≤7 days, then maintain dose level. If resolved in >7 days, then reduce ribociclib dose to the next lower dose level.	Dose interruption until recovery to grade ≤2. Re-initiate everolimus at the same dose level. If ribociclib is interrupted/ discontinued, everolimus should also be interrupted/discontinued. Resume everolimus at same dose level if ribociclib is resumed at either the same or lower dose.
Grade 4 (ANC < 0.5 x 10 ⁹ /L)	Dose interruption until recovery to ≥1.0x10 ⁹ /L. Re-initiate ribociclib at the next lower dose level. If toxicity recurs at grade 4, discontinue ribociclib+everolimus	Dose interruption until recovery to grade ≤2. Re-initiate everolimus at the next lower dose level. If toxicity recurs at grade 4, discontinue ribociclib+everolimus
Febrile neutropenia Grade 3 (ANC < 1.0 x 10 ⁹ /L, with a single temperature of ≥ 38.3 °C (101°F) or a sustained temperature of ≥ 38 °C (100.4°F) for more than one hour)	Dose interruption until improvement of ANC ≥1.0x10 ⁹ /L (≤Grade 2) and no fever. Restart at the next lower dose level. If febrile neutropenia recurs, discontinue ribociclib +everolimus.	Dose interruption until improvement of ANC ≥1.0x10 ⁹ /L (≤Grade 2) and no fever. Re-initiate everolimus at the next lower dose level. If febrile neutropenia recurs, discontinue ribociclib +everolimus.
Febrile neutropenia Grade 4 Life-threatening consequences; urgent intervention indicated	Discontinue treatment.	Discontinue treatment.

Worst toxicity (CTCAE 4.03 Grade)*	Regimen Modifications for Ribociclib Management Recommendations	Regimen Modifications for Everolimus Management Recommendations
Thrombocytopenia		
Grade 1 (PLT < LLN - $75 \times 10^9/L$)	Continue regimen	Continue regimen
Grade 2 (PLT < 75 and $\geq 50 \times 10^9/L$)	Dose interruption until recovery to grade ≤ 1 . Re-initiate ribociclib at the same dose.	Dose interruption until recovery to grade ≤ 1 . Re-initiate everolimus at the same dose.
Grade 3 (PLT < 50 and $\geq 25 \times 10^9/L$)	Dose interruption until recovery to grade ≤ 1 . Re-initiate ribociclib at the same dose level. If toxicity recurs at grade 3, temporary dose interruption until recovery to grade ≤ 1 and reduce ribociclib to the next lower dose level.	Dose interruption until recovery to grade ≤ 1 . Re-initiate everolimus at the next lower dose level. If toxicity recurs at grade 3, temporary dose interruption until recovery to grade ≤ 1 and reduce everolimus to the next lower dose level.
Grade 4 (PLT < $25 \times 10^9/L$)	Dose interruption until recovery to grade ≤ 1 . Re-initiate ribociclib at the next lower dose level. If toxicity recurs at grade 4: discontinue ribociclib	Dose interruption until recovery to grade ≤ 1 . Re-initiate everolimus at the next lower dose level. If toxicity recurs at grade 4: discontinue everolimus

Worst toxicity (CTCAE 4.03 Grade)*	Regimen Modifications for Ribociclib Management Recommendations	Regimen Modifications for Everolimus Management Recommendations
HEPATOTOXICITY (BILIRUBIN, SGPT/ALT, SGOT/AST)		
Total Bilirubin** without ALT/AST increase above baseline value (for patients with Gilbert Syndrome these dose modifications apply to changes in direct (conjugated) bilirubin only)		
Grade 1 (> ULN and ≤ 1.5 x ULN)	Maintain dose level with liver function test (LFTs)*** monitored as per protocol Confirm at 48-72 hours later	Continue regimen
Grade 2 (> 1.5 and ≤ 3.0 x ULN) with ALT or AST ≤ 3.0 x ULN	Dose interruption of ribociclib If resolved to ≤ grade 1 in ≤21 days, then maintain dose level. If resolved to ≤ grade 1 in >21-28 days or toxicity recurs, then reduce 1 dose level. Repeat liver enzymes and bilirubin tests twice weekly for 2 weeks after dose resumption. If toxicity recurs after 1 dose reduction, or recovery to < grade 1 in > 28 days, discontinue ribociclib+everolimus.	If ribociclib is interrupted/discontinued, everolimus should also be interrupted/discontinued. Resume everolimus at same dose level if ribociclib is resumed at either the same or lower dose. If toxicity recurs after 1 dose reduction, or recovery to ≤ grade 1 in > 28 days, discontinue ribociclib+everolimus.
Grade 3 (> 3.0 and ≤ 10.0 x ULN) with ALT or AST ≤ 3.0 x ULN	Dose interruption of ribociclib, until resolved to ≤ grade 1, then lower 1 dose level of ribociclib Repeat liver enzyme and bilirubin tests twice weekly for 2 weeks after dose resumption If resolved to ≤ grade 1 in > 28 days or toxicity recurs, discontinue ribociclib+everolimus	If ribociclib is interrupted/discontinued, everolimus should also be interrupted/discontinued. Resume everolimus at same dose level if ribociclib is resumed at lower dose level. If toxicity recurs after 1 dose reduction, or recovery to ≤ grade 1 in > 28 days, discontinue ribociclib+everolimus.
Grade 4 (> 10.0 x ULN)	Permanently discontinue patient from ribociclib+everolimus	
Confounding factors and/or alternative causes for increase of total bilirubin should be excluded before dose interruption/reduction. They include but are not limited to: evidence of liver metastases, evidence of obstruction, such as elevated ALP and GGT typical of gallbladder or bile duct disease, hyperbilirubinemia due to the indirect component only (i.e. direct bilirubin component ≤ 1 x ULN) due to hemolysis or Gilbert Syndrome, other pharmacologic treatment, viral hepatitis, alcoholic or autoimmune hepatitis, other hepatotoxic drugs. For patients with Gilbert Syndrome, these dose modifications apply to changes in direct bilirubin only. Bilirubin will be fractionated if elevated.		

Worst toxicity (CTCAE 4.03 Grade)*	Regimen Modifications for Ribociclib Management Recommendations	Regimen Modifications for Everolimus Management Recommendations
AST or ALT		
AST or ALT without bilirubin elevation >2 x ULN		
Same grade as baseline or increase from baseline grade 0 to grade 1 (confirmed 48 to 72 hours later)	Maintain dose level with LFTs*** monitored per protocol if same grade as baseline or bi-weekly in case of increase from baseline grade 0 to 1.	Continue regimen
Increase from baseline grade 0 or 1 to Grade 2 (> 3.0 and ≤ 5.0 x ULN)	Dose interruption of ribociclib: If resolved to ≤ baseline value in ≤ then 21 days, then maintain dose level If resolved to ≤ baseline value in > then 21 days or toxicity recurs, then reduce 1 dose level of ribociclib. Repeat liver enzymes and bilirubin tests twice weekly for 2 weeks after dose resumption. If toxicity recurs after 1 dose reduction or recovery to ≤ baseline value is >28 days, discontinue ribociclib+everolimus.	If ribociclib is interrupted/discontinued, everolimus should also be interrupted/discontinued. Resume everolimus at same dose level If toxicity recurs after 1 dose reduction, or recovery to ≤ grade 1 in > 28 days, discontinue ribociclib+everolimus.
Increase from baseline grade 0 or 1 to grade 3 (> 5.0 – 20.0 x ULN)	Dose interruption of ribociclib until resolved ≤ baseline value then reduce 1 dose level of ribociclib. Repeat liver enzymes and bilirubin tests twice weekly for 2 weeks after dose resumption. If toxicity recurs after 1 dose reduction or recovery to ≤ baseline value is >28 days ribociclib+everolimus.	If ribociclib is interrupted/discontinued, everolimus should also be interrupted/discontinued. Resume everolimus at same dose level if ribociclib is resumed at either the same or lower dose. If toxicity recurs after 1 dose reduction, or recovery to ≤ grade 1 in > 28 days, discontinue ribociclib+everolimus.
Increase from baseline grade 2 to grade 3 (> 5.0 – 20.0 x ULN)	Dose interruption of ribociclib until resolved to ≤ baseline grade, then lower 1 dose level of ribociclib Repeat liver enzyme and bilirubin tests twice weekly for 2 weeks after dose resumption If toxicity recurs after 1 dose reduction or recovery to ≤ baseline grade is > 28 days, discontinue ribociclib+everolimus.	If ribociclib is interrupted/discontinued, everolimus should also be interrupted/discontinued. Resume everolimus at same dose level if ribociclib is resumed at either the same or lower dose. If toxicity recurs after 1 dose reduction, or recovery to ≤ grade 1 in > 28 days, discontinue ribociclib+everolimus.
Grade 4 (> 20.0 x ULN) without bilirubin elevation to > 2.0 x ULN	Discontinue study treatment.	Discontinue study treatment.
AST or ALT and concurrent Total Bilirubin		
For patients with normal ALT and AST and total bilirubin at baseline: AST or ALT >3.0 x ULN combined with total bilirubin > 2 x ULN without evidence of cholestasis Or	Discontinue study treatment.	Discontinue study treatment.

Worst toxicity (CTCAE 4.03 Grade)*	Regimen Modifications for Ribociclib Management Recommendations	Regimen Modifications for Everolimus Management Recommendations
For patient with elevated AST or ALT or total bilirubin at baseline: baseline: [AST or ALT >2 x baseline AND >3.0x ULN] OR [AST or ALT 8.0 x ULN]- whichever is lower- combined with [total bilirubin > 2 x baseline AND >2.0 x ULN]		
Confounding factors and/or alternative causes for increased transaminases should be excluded before dose interruption/reduction. They include but are not limited to: concomitant medications, herbal preparations or dietary supplements, infection, hepato-biliary disorder or obstruction, new or progressive liver metastasis, and alcohol intake.		

Worst toxicity (CTCAE 4.03 Grade)*	Regimen Modifications for Ribociclib Management Recommendations	Regimen Modifications for Everolimus Management Recommendations
QTcF Prolongation		
For all grades	
Check the quality of the ECG and the QT value and repeat if needed.
 
Perform analysis of serum electrolytes (K+, Ca++, Phos Mg++). If outside of normal range, interrupt ribociclib administration, correct with supplements or appropriate therapy as soon as possible, and repeat electrolytes until documented as normal.
 
Review concomitant medication usage for the potential to inhibit CYP3A4 and/or to prolong the QT interval.
 
Check compliance with correct dose and administration of ribociclib. (Consider collecting a time matched PK sample: record date/time of last study drug dose.)
	N/A
Grade 1 (QTc 450-480 ms)	Perform steps 1-4 as directed in "For All Grades." Continue regimen.	Continue regimen.
Grade 2 (QTc 481-500 ms)	
Interrupt ribociclib. Perform steps 1-4 as directed in "For All Grades."
 
Perform a repeat ECG one hour after the first QTcF of ≥ 481 ms.
 
• If QTcF < 481 ms, restart ribociclib at the same dose. No dose adjustment required for first occurrence.• If QTcF remains ≥ 481 ms, repeat ECG as clinically indicated until the QTcF returns to < 481 ms. Ribociclib should be reduced by 1 dose level• If QTcF ≥ 481 ms recurs, ribociclib should again be reduced by 1 dose level. 
Repeat ECGs 7 days and 14 days after dose resumption (then as clinically indicated) for any patient who has therapy interrupted due to QTcF ≥ 481 ms.
	If ribociclib is interrupted/discontinued, everolimus should also be interrupted/discontinued. Resume everolimus at same dose level if ribociclib is resumed at same or lower dose level.

Worst toxicity (CTCAE 4.03 Grade)*	Regimen Modifications for Ribociclib Management Recommendations	Regimen Modifications for Everolimus Management Recommendations
Grade 3 (QTc \geq 501 ms on at least two separate ECGs)	
Interrupt ribociclib. Perform steps 1-4 as directed in "For All Grades."
 
Perform a repeat ECG within one hour of the first QTcF of \geq501 ms.
 
• If QTcF remains \geq501 ms, consult with a cardiologist (or qualified specialist) and repeat cardiac monitoring as indicated until the QTcF returns to $<$481 ms.• If QTcF returns to $<$481 ms, ribociclib should be reduced by 1 dose level (please refer to the dosing schedule table).• If QTcF remains \geq 481 ms after performing steps 1-4 as directed in "For All Grades," discontinue ribociclib. 
Repeat ECGs 7 days and 14 days after dose resumption for any patient who has therapy interrupted due to QTcF \geq501 ms.
 
If QTcF of \geq501 ms recurs, discontinue ribociclib
	If ribociclib is interrupted/discontinued, everolimus should also be interrupted/discontinued. Resume everolimus at same dose level if ribociclib is resumed at lower dose level.
Grade 4 (QT/QTc \geq 501 or $>$ 60 ms change from baseline and Torsades de pointes or polymorphic ventricular tachycardia, or signs/symptoms of serious arrhythmia, unexplained syncope)	
Discontinue ribociclib+everolimus. Perform steps 1-4 as directed in "For All Grades."
 
Obtain local cardiologist consultation (or qualified specialist) and repeat cardiac monitoring as indicated until the QTcF returns to $<$481 ms.
	

Worst toxicity (CTCAE 4.03 Grade)*	Regimen Modifications for Ribociclib Management Recommendations	Regimen Modifications for Everolimus Management Recommendations
Stomatitis		
Grade 1 Minimal symptoms; normal diet	No dose adjustment required. Manage with non-alcoholic or salt water (0.9%) mouthwash several times per day	
Grade 2 Symptomatic but can eat and swallow modified diet	If everolimus is interrupted/discontinued, ribociclib should also be interrupted/discontinued. Resume ribociclib at same dose level if everolimus is resumed at same or lower dose level.	Interrupt everolimus until recovery to Grade ≤ 1. Reinitiate everolimus at same dose. If recurs at Grade 2, interrupt dose until recover to Grade ≤ 1. Resume at 50% of previous dose; change to every other day dosing if the reduced dose is lower than the lowest available strength. Manage with topical analgesic mouth treatments.
Grade 3 Symptomatic and unable to adequately eat or hydrate orally	If everolimus is interrupted/discontinued, ribociclib should also be interrupted/discontinued. Resume ribociclib at same dose level if everolimus is resumed at lower dose level.	Dose interruption of everolimus until recovery to Grade < 1. Resume at 50% of previous dose; change to every other day dosing if the reduced dose is lower than the lowest available strength.
Grade 4 Symptoms associated with life-threatening consequences	Discontinue ribociclib+everolimus	Discontinue everolimus and treat with appropriate medical therapy
Non-infectious pneumonitis		
Grade 1 Asymptomatic, radiographic findings only	No dose adjustment required. Initiate appropriate monitoring.	
Grade 2 Symptomatic but not interfering with Activities of Daily Living (ADL)	If everolimus is interrupted/discontinued, ribociclib should also be interrupted/discontinued. Resume ribociclib at same dose level if everolimus is resumed at same or lower dose.	Consider dose interruption of everolimus. Rule out infection and consider treatment with corticosteroids until symptoms improve to Grade < 1 Resume at 50% of previous dose; change to every other day dosing if the reduced dose is lower than the lowest available strength. Discontinue everolimus if failure to recover within 4 weeks.
Grade 3 Symptomatic, interfering with ADL; Oxygen indicated	If everolimus is interrupted/discontinued, ribociclib should also be interrupted/discontinued. Resume ribociclib at same dose level if everolimus is resumed at same or lower dose.	Dose interruption of everolimus until symptoms improve to Grade < 1 Rule out infection and consider treatment with corticosteroids Resume at 50% of previous dose; change to every other day dosing if the reduced dose is lower than the lowest available strength. If toxicity recurs at Grade 3, consider discontinuation

Worst toxicity (CTCAE 4.03 Grade)*	Regimen Modifications for Ribociclib Management Recommendations	Regimen Modifications for Everolimus Management Recommendations
Grade 4 Life-threatening, ventilator support indicated	Discontinue ribociclib+everolimus	Discontinue everolimus, rule out infection, and consider treatment with corticosteroids.
Metabolic Events (hyperglycemia, dyslipidemia)		
Grade 1	If everolimus is interrupted/discontinued, ribociclib should also be interrupted/discontinued. Resume ribociclib at same dose level if everolimus is resumed at same or lower dose.	If toxicity is tolerable, no dose adjustment required. Initiate appropriate medical therapy and monitor.
Grade 2	If everolimus is interrupted/discontinued, ribociclib should also be interrupted/discontinued. Resume ribociclib at same dose level if everolimus is resumed at same or lower dose.	If toxicity is tolerable, no dose adjustment required. Manage with appropriate medical therapy and monitor.
Grade 3	If everolimus is interrupted/discontinued, ribociclib should also be interrupted/discontinued. Resume ribociclib at same dose level if everolimus is resumed at lower dose.	Dose interruption of everolimus until recovery to Grade < 1. Resume at 50% of previous dose; change to every other day dosing if the reduced dose is lower than the lowest available strength. Manage with appropriate medical therapy and monitor.
Grade 4	Discontinue ribociclib+everolimus	Discontinue everolimus and treat with appropriate medical therapy
All other adverse reactions Non-hematologic (excluding metabolic events)		
Grade 1	If everolimus is interrupted/discontinued, ribociclib should also be interrupted/discontinued. Resume ribociclib at same dose level if everolimus is resumed at same or lower dose.	If toxicity is tolerable, no dose adjustment required Initiate appropriate medical therapy and monitor.
